D.1.1. Dexamethasone. Dexamethasone was chosen over other corticosteroids because it is a synthetic, long-acting, potent corticosteroid with minimal mineralocorticoid activity. It is commonly used in the oncology setting for management of fatigue, pain, anorexia, and nausea and vomiting (Chow *et al.* 2015, Hesketh *et al.* 2016, Yennurajalingam *et al.* 2013). Moreover, dexamethasone demonstrated promising activity in our preliminary trial (Hui *et al.* 2016a) (Section D.1.1.3).

D.1.2. Oral route. The oral route was selected instead of the inhaled route because dexamethasone is expected to exert its effect both peripherally and centrally. Absorption of inhaled corticosteroid may be less reliable. The oral route is also more convenient than the intravenous route in the ambulatory setting. Furthermore, our preliminary data (Section D.1.1.3) suggest that oral dexamethasone was associated with dyspnea improvement.

D.1.3. Dosing. In our preliminary study, dexamethasone was given at a dose of 8 mg orally twice daily for 4 days, followed by 4 mg twice daily for 3 days, and the peak effect was reached within 4 days. We observed no significant adverse effects in the dexamethasone group at this dose compared with placebo. Thus, we would like to extend the use of dexamethasone at a dose of 8 mg twice daily to 7 days to evaluate its longer-term effects. This dose is justified because high-dose prednisone (i.e., 100 mg daily, which is equivalent to 16 mg of dexamethasone) is often given in the oncology setting as part of cancer treatment.

D.1.4. Tapering. The tapering schedule is designed according to routine clinical practice, which reduces the dexamethasone dose to half (4 mg twice daily, then 2 mg twice daily) before stopping to minimize cortisol deficiency due to hypothalamic-pituitary-adrenal axis suppression. Given that the total duration of treatment with dexamethasone is 2-4 weeks, we do not expect substantial adverse effects.

[figure not shown]

Figure 2. Study Flow Chart

D.1.5. Study duration and endpoint. The duration to the primary endpoint will be 7 ± 2 days of high-dose dexamethasone/placebo. This was carefully chosen over longer time frames because (1) dyspnea is highly distressing and rapid symptomatic relief is essential; and (2) prolonged use of high-dose dexamethasone may result in greater side effects. We will assess the longer-term use of dexamethasone at lower doses for up to 4 weeks as part of our secondary analysis.

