| 3. Previous allergic reactions to dexamethasone |
| 4. Diagnosis of diabetes mellitus uncontrolled with oral hypoglycemic agents or insulin |
| 5. Postsurgical open wound that has not healed at the time of enrollment |
| 6. Any infection requiring antibiotics at the time of study enrollment |
| 7. Major surgery within the past 2 weeks |
| 8. Megestrol use at the time of study enrollment |
| 9. Neutropenia (absolute neutrophil count $<1.0 \times 10^9/L$) at the time of study enrollment (bloodwork is not required if patient did not have chemotherapy within past 2 weeks) |
| 10. Currently receiving or expected to start cytotoxic chemotherapy or immunotherapy within 1 week of study enrollment and additional dexamethasone cannot be used concurrently as per attending oncologist |
| 11. Severe anemia (hemoglobin <8 g/L) not corrected prior to study enrollment (bloodwork is not required if patient did not have chemotherapy within past 2 weeks) |
| 12. COPD exacerbation at the time of study enrollment |
| 13. Heart failure exacerbation at the time of study enrollment |
| 14. Expected to undergo therapeutic thoracentesis in the next 2 weeks |
| 15. High anxiety score ($\geq 15/21$) on the Hospital Anxiety and Depression Scale (HADS) |
| 16. Chronic systemic corticosteroid use (>14 days) at the time of study enrollment |
| 17. Any expected corticosteroid use during study enrollment at higher doses than will be used in this study |

D.3. Recruitment. The research staff will screen patients in the outpatient setting to identify potential candidates. For patients who are eligible on the basis of chart review, our research staff will approach them either in-person, or through remote methods for permission to conduct further screening for eligibility. Remote methods will consist of phone or vetted video-conferencing platforms (WebEx, Skype, FaceTime, or Zoom) to call potential participants to explain the study and gauge interest. If the participant wishes to participate, MyChart or e-mail will be used to send the consent form and research staff will obtain consent through this method.

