D.5. Study interventions. Dexamethasone is a commonly used medication in cancer patients. It is approved by the US Food and Drug Administration for treatment of multiple indications, including allergic disorder (including asthma), cerebral edema associated with primary or metastatic brain tumor, craniotomy, or head injury, collagen disease, disorder of ear, disorder of endocrine system, disorder of eye, disorder of gastrointestinal tract, disorder of hematopoietic structure, disorder of respiratory system (treatment of berylliosis, fulminating or disseminated pulmonary tuberculosis (when used concurrently with appropriate antituberculosis therapy), idiopathic eosinophilic pneumonias and symptomatic sarcoidosis, Loeffler's syndrome not manageable by other means and aspiration pneumonitis), disorder of skin, exacerbation of multiple sclerosis, hypercalcemia of malignancy, idiopathic thrombocytopenic purpura, inflammatory disorder of musculoskeletal system, macular retinal edema, mycosis fungoides, neoplastic disease, palliative management of leukemias and lymphomas, nephrotic syndrome, Idiopathic or due to lupus erythematosus without uremia, non-infectious posterior uveitis, trichinosis with neurologic or myocardial involvement, tuberculosis of meninges with subarachnoid block or impending block when used concurrently

with antituberculosis therapy. However, it has not been specifically approved for management of dyspnea.

Our study proposes to use oral dexamethasone for the management of dyspnea. Based on our preliminary data, the intervention arm will receive dexamethasone at a dose of 8 mg given orally twice daily for 7 days, then 4 mg given orally twice daily for 7 days. We do not plan to seek FDA approval for the new indication of dyspnea.

The control arm will receive placebo capsules prepared by a compounding pharmacy (e.g. Greenpark Pharmacy) identical in appearance to dexamethasone 4 mg capsules, and will be instructed to take two capsules twice a day for 7 days, followed by one capsule twice a day for 7 days.

In the open label phase, patients assigned to either arm will be asked to take dexamethasone 4 mg orally twice a day for 7 days, then 2 mg orally twice a day for 7 days. Both dexamethasone and placebo capsules used throughout this study will be dispensed by Investigational Pharmacy at MD Anderson. Dexamethasone/placebo capsules and open-label tablets will be provided free of charge to patients during the study period.

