D.8. Medication use during study and cointerventions. During the 2-week blinded phase, patients may continue their usual treatments for dyspnea, including opioids, supplemental oxygen, and bronchodilators. These treatments will be documented and adjusted for in the analysis. Our eligibility criteria are designed to specifically exclude patients who have reversible causes of acute dyspnea, such as pleural effusions, COPD exacerbations, or pneumonia.

D.9. Research staff training. An orientation will be held with research staff involved in this study to introduce them with the study design, and standardize the provision of each intervention. We will also conduct principal investigator research meetings 2-4x/month.

D.10. Patient Safety, Monitoring, and Confidentiality. Prior to study initiation, all research staff participating in this study will receive an orientation to the devices and forms in this study to ensure consistent assessments. During the study, trained research staff will be performing study assessments and monitoring the patient carefully throughout the study period. In addition to daily phone calls, or contact through other remote methods, patients will be given the contact information of the research staff in case they develop any significant adverse effects, and will be treated as they arise as per clinical practice. The study may be discontinued at the discretion of the treating physician or study principal investigator. Regulatory monitoring will be provided by the principal investigator, the Institutional Review Board, and the Data Safety

and Monitoring Board. Patient confidentiality will be ensured by use of patient initials, secure storage of clinical data, and anonymous reporting.

Table 3. Study assessments

| Assessment | Baseline (in person) | Days 0-6 (phone or remote contact) | Day 7±2 (in per- son ¹¹) | Days 8- 13 (phone or re- mote contact) | Day 14±2 (in per- son ¹¹) | Day 28±2, Day 42±2 (phone or remote contact) |
|--|-------------------------|---|--|---|--|--|
| Screening (Appendix A, B) | ✓ | | | | | |
| Demographics (Appendix C) | ✓ | | | | | |
| Dyspnea NRS score (primary outcome: intensity; secondary: unpleasantness; assessment requires <1min) ¹ (Appendix D) | ✓ | ✓ | ✓ | ✓ | ✓ | ✓ |
| Personalized dyspnea goals (<1min) ² (Appendix I) | ✓ | | | | ✓ | |
| Biomarkers (blood draw, 15min) ³ (Appendix J) | ✓ | | ✓ | | ✓ | |

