E.2.3. Secondary objective #2. The primary endpoint will be the baseline to day 7 difference in dyspnea NRS (>1.0 is considered clinically significant). We will use logistic regression analysis to identify independent predictors of this outcome, including baseline dyspnea NRS, restrictive or obstructive lung disease pattern, MIP, sex, and baseline inflammatory cytokine levels (IL-1 β , IL-6, IL-8, IL-10, and TNF- α). We will plot the data and use residual analyses to verify assumptions of the model and take appropriate actions if they appear to be validated (e.g., transforming the data). We will use the variance inflation factor to identify collinearity. With 116 dexamethasone-treated patients, we would have at least 80% power to detect an odds ratio of 2.5 (for a one-unit change in a normally distributed marker) if the response probability is at least 30% (assuming 5% alpha and a correlation between the marker and the other factors in the model of 0.30). As an exploratory analysis, we will perform a similar analysis to that described for the primary endpoint to determine whether patients achieved their personal goal in dyspnea improvement. We will perform a similar exploratory linear regression analysis using

the difference between the day 7 and baseline dyspnea NRS scores as the endpoint. Additional exploratory correlative analyses will be conducted for changes in inflammatory markers between day 7 and baseline.

E.2.4. Secondary objective #3. We will calculate summary statistics for duration of dexamethasone dosing and cumulative dexamethasone dose. Two-sample t-tests or Wilcoxon rank sums tests will be used to examine whether binary events, such as adverse events, are associated with higher doses or duration of dexamethasone. If number of hospital admissions follows a Poisson distribution or zero-inflated Poisson distribution, we will use the appropriate model to examine the association of number of hospitalizations with cumulative dose and duration. All patients, regardless whether they received placebo, will be used to examine dose and duration initially. In these analyses, dose and duration for patients who received placebo will be set to zero. In a second set of analyses, only those patients who received dexamethasone will be included in the analyses. All testing will be 2-sided with 5% alpha. We will consider limiting the false detection rate to 10%.

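### Exclusions 16 and 17 allow short-term or study-dose open corticosteroid in both arms, and section E.2.4 sets exposure to zero for every placebo patient

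*Combined protocol and SAP*

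**What the plan says.** Three exclusions in Table 2 concern corticosteroids.

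- Exclusion 16: "Chronic systemic corticosteroid use (>14 days) at the time of study enrollment".
- Exclusion 17: "Any expected corticosteroid use during study enrollment at higher doses than will be used in this study".
- Exclusion 10 concerns patients on, or about to start, chemotherapy or immunotherapy. It applies only if "additional dexamethasone cannot be used concurrently as per attending oncologist".

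The blinded active regimen in section D.5 is "dexamethasone at a dose of 8 mg given orally twice daily for 7 days, then 4 mg given orally twice daily for 7 days". In the open-label phase, patients from either arm are asked to take 4 mg twice daily for 7 days, then 2 mg twice daily for 7 days.

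On other treatment, section D.8 says that "patients may continue their usual treatments for dyspnea, including opioids, supplemental oxygen, and bronchodilators", and adds: "These treatments will be documented and adjusted for in the analysis". Corticosteroids are not named there. Section D.7.1 collects medications at baseline, with opioids and bronchodilators as examples. The primary model in E.2.1 compares day 7 scores by arm and adjusts for baseline score. Randomization is stratified by baseline dyspnea and site (D.4).

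For the adverse-event and dose analysis, E.2.4 first uses all patients, and in that set "dose and duration for patients who received placebo will be set to zero". A second set is limited to patients who received dexamethasone.

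**The concern.** The comparator is no dexamethasone, but exclusion 17 is measured against the active-arm dose. A patient in a second week of systemic corticosteroid, at a dose no higher than the study's, passes both 16 and 17. No section washes this use out, prohibits it or puts it in the primary model.

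Three results could be affected.

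- **Primary comparison.** The difference could shrink, and a null result would be harder to interpret.
- **Dose and adverse events (secondary objective #3).** Placebo patients with real corticosteroid exposure would be analysed as unexposed.
- **Predictive markers (secondary objective #2).** Baseline cytokines could be drawn while a patient is already taking a drug class that, by the protocol's own rationale, modulates the inflammatory response.

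**Working it through.** **1. Who can enter.** Use of 14 days or less passes exclusion 16. Expected use at or below the study dose passes exclusion 17. The week 1 study dose is 2 × 8 = 16 mg/day. Section D.1.3 equates prednisone 100 mg daily with 16 mg dexamethasone and says it is often given as part of cancer treatment. On a week 1 reading this is not a higher dose, so it passes. The ceiling is not a single number: it is 16 then 8 mg/day in the blinded phase and 8 then 4 mg/day in the open-label phase. Exclusion 17 does not say which dose or period it means, and these passages need to be reconciled.

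**2. The plan's own sample size.** Section E.1 uses a difference of 1.0, SD 2.0, two-sided 5%, 2:1 allocation and 80% power, and gives 116 + 58 = 174.

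- Placebo n = (1.960 + 0.842)² × 2.0² × (1 + 1/2) / 1.0² = 7.85 × 6 = 47.1, so 48. The total is 48 + 96 = 144.
- With 116 + 58, SE = 2.0 × √(1/116 + 1/58) = 0.3216, and 1.0/0.3216 = 3.11. Power is 87% (noncentral t, 0.871).

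The stated 174 therefore gives about 87%, not 80%. That is a separate matter and on the safe side, but it provides some reserve here.

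**3. Dilution as an assumed range.** Let c be the share of patients affected by open corticosteroid and r the fraction of the study effect lost in them. The expected difference is 1.0 × (1 − c × r). A 10% loss arises from 10% of patients with r = 1, or from 20% with r = 0.5. The documents give neither c nor r.

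| Effect lost (c × r) | Difference | Difference / SE | Power, single test | Power, stated interim boundaries |
|---|---|---|---|---|
| 0% | 1.0 | 3.11 | 87% (0.871) | 86% |
| 10% | 0.9 | 2.80 | 80% (0.795) | 78% |
| 20% | 0.8 | 2.49 | 70% (0.696) | 68% |
| 30% | 0.7 | 2.18 | 58% (0.581) | 56% |

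The last column is a simulation with the boundaries in E.2.7, reading futility as two-sided p and binding. For the single test, 80% power needs a ratio of 1.960 + 0.842 = 2.80. Since 2.80/3.11 = 0.90, the planned power is lost only beyond a loss of about 10%.

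**4. Exposure in E.2.4.** Full doses from section D.5:

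| | Blinded | Open-label | Total |
|---|---|---|---|
| Dexamethasone arm | 16 × 7 + 8 × 7 = 168 mg | 8 × 7 + 4 × 7 = 84 mg | 252 mg in 28 days |
| Placebo arm, actual | 0 | 84 mg | 84 mg in 14 days |
| Placebo arm, as coded | 0 | 0 | 0 |

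Up to day 14, zero is right for study drug in the placebo arm, but wrong for any non-study corticosteroid. Table 3 also schedules adverse effects at day 28 and day 42. If those are counted, a placebo patient who took the open-label course is entered 84 mg and 14 days too low.

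**The case against.** Several arguments limit the point, and most of them stand.

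- **Patients already on steroid carry its effect in their baseline.** They must still average at least 4 on the dyspnea NRS over the past week. Section D.1.3 puts the pilot's peak effect within 4 days, and E.2.1 adjusts for baseline. A reader might infer that such a placebo patient gains the full study effect by day 7; the documents do not support that. Dilution needs either steroid started after baseline or study drug adding less on top of it. If the effects were fully additive and use was balanced, the difference would not shrink.
- **Both arms are affected alike.** Eligibility is settled before randomization, so the gap creates no imbalance by itself.
- **Exclusion 10 is a compatibility check.** A reader might infer that it selects patients who receive outside dexamethasone. It shows only that the oncologist accepts the addition of dexamethasone.
- **Section D.1.4 is not contradicted.** It says "Given that the total duration of treatment with dexamethasone is 2-4 weeks", and one might add up to 14 days of earlier use and call that a conflict. The sentence describes study treatment: 2 weeks for placebo patients through the open-label phase, 4 weeks for the active arm.
- **Some recording exists.** D.7.1 collects baseline medications, its examples are not exhaustive, and daily contacts are planned. This stands in part: corticosteroids are not named, and steroid given for nausea is not a dyspnea treatment under D.8. Adjusting for use that starts after randomization would not restore the contrast.
- **E.2.4 has a second analysis.** Restricting to dexamethasone recipients avoids the placebo zero, but it does not correct the first analysis.
- **Broad entry is deliberate.** Section D.2 gives generalizability as the aim, which is a legitimate reason to keep these patients.

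**Conclusion.** The gap in exclusions 16 and 17 is in the text, and no other section closes it. That it may dilute the primary contrast is a reasonable concern; that it will do so, or by how much, cannot be shown from the documents. The power range rests on an assumed loss of effect, and power falls below the planned 80% only beyond a loss of about 10%. It would go too far to say that a negative trial must reflect contamination, or that the exclusions have to be rewritten.

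The exposure rule in E.2.4 is the firmer part. Setting every placebo patient to zero misstates exposure for those on open corticosteroid, and for those taking open-label dexamethasone once day 28 and 42 events are included. The second of these needs no assumption about outside use, because both arms are asked to take the open-label course.

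These changes should be made. They are cheap and they improve how the primary and secondary results can be read.

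**What to change.** 1. **E.2.4.** Replace the zero with each patient's actual cumulative corticosteroid dose and duration up to the adverse-event assessment analysed. Count blinded, open-label and non-study corticosteroid in dexamethasone equivalents, with the conversion factors fixed in advance.
2. **Recording.** Name corticosteroids in D.7.1 and D.8. Before randomization, record whether the patient is on, or scheduled for, corticosteroid. Capture agent, dose and dates on the daily contacts through day 13 and at the day 14, 28 and 42 assessments. Pill counts are scheduled only at days 7 and 14, so open-label intake must be asked about.
3. **E.2.1.** Pre-specify a sensitivity analysis of the day 7 endpoint in patients neither on nor scheduled for corticosteroid before randomization. Because the subset is defined before randomization, the randomized comparison is preserved. It does not remove steroid started unexpectedly later.
4. **E.2.3.** Flag baseline cytokine samples drawn on corticosteroid and repeat the marker analysis without them.

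The cost is one added data field, a little more analysis, and lower precision in the restricted analyses. For example, if 20% of patients were set aside, SE would be 0.3216/√0.8 = 0.360 and 1.0/0.360 = 2.78. Since 2.78 − 1.96 = 0.82, power for a 1.0-point difference would be about 79%.

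Whether to tighten exclusions 16 and 17 is for the sponsor to weigh against generalizability and recruitment. In either case, the dose and period that exclusion 17 refers to should be reconciled with the changing dose in section D.5.

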
Table 1. Change in dyspnea in the dexamethasone and placebo arms (statistically significant values in boldface type)

| Variable | Dexamethasone | | | Placebo | | | Mean difference between arms (95% CI) |
|---|---------------|-------------|--|---------|-------------|--|---------------------------------------|
| | N | Mean (SD) | Mean change from baseline (95% CI) | N | Mean (SD) | Mean change from baseline (95% CI) | |
| ESAS dyspnea (average over the past 24 hours) | | | | | | | |
| Baseline | 19 | 5.0 (2.1) | - | 19 | 4.7 (1.5) | - | - |
| Day 4 | 15 | 3.3 (1.8) | -1.9 (-3.3 to -0.5), P = 0.01 | 15 | 3.7 (2) | -0.7 (-2.1 to 0.6), P = 0.38 | -1.2 (-3 to 0.6) |
| Day 7 | 16 | 3.6 (2.6) | -1.8 (-3.2 to -0.3), P = 0.02 | 14 | 3.3 (2.1) | -1.3 (-2.4 to -0.2), P = 0.03 | -0.5 (-2.2 to 1.2) |
| EORTC Quality of Life Questionnaire-C30 Dyspnea (over the past week) | | | | | | | |
| Baseline | 19 | 57.9 (29.1) | - | 19 | 49.1 (20.4) | - | - |
| Day 4 | 15 | 46.7 (16.9) | -15.6 (-29.3 to -1.8), P = 0.04 | 15 | 46.7 (24.6) | 0 (-14 to 14), P > 0.99 | -15.6 (-33.5 to 2.3) |
| Day 7 | 16 | 47.9 (17.1) | -10.4 (-21.1 to 0.3), P = 0.08 | 13 | 43.6 (16) | -5.1 (-19 to 8.8), P = 0.69 | -5.3 (-21.2 to 10.6) |

D. Experimental Approach

D.1. Overall Study design. This is a parallel, two-arm, double-blind, randomized, placebo-controlled trial of dexamethasone for cancer patients with dyspnea (Figure 2). We plan to enroll 201 patients (134 in the dexamethasone group and 67 in the placebo group, Section D.1.11.1), with a target enrollment rate of five to six patients per month. The eligibility criteria are shown in Table 2. After providing written informed consent, enrolled patients will complete baseline questionnaires to assess the severity of their dyspnea. Study drug may be mailed to participants. At MD Anderson, sometimes patients do not have time to pick up study medication after enrollment and do not start the study until a few days later. For HHS/LBJ, patients will get their medication via MD Anderson pharmacy so their medications will also need to be mailed to them. On the basis of our experience, we believe that the proposed study is feasible and will not add an undue burden for patients. The rationale for the proposed study design is as follows.

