⁷The EORTC QLQ-C30 is a well-validated quality-of-life assessment for patients with cancer, consisting of 30 questions that encompass three symptom scales (pain, fatigue, and nausea/vomiting) and six questions about single symptoms, as well as five functional scales (physical, cognitive, role, emotional, and social) and one scale assessing global health status/quality of life. Each scale consists of two to five items, and all items have four response categories (not at all, a little, quite a bit, and very much), except for two items assessing overall health status/quality of life, which use a 7-point scale.

⁸In addition to clinician assessment of adverse effects according to CTCAE v4.03, adverse effects related to the use of dexamethasone, such as heartburn (F, S), nausea (F, S), pain in the abdomen (F, S, I), vomiting (F, S), arm/leg swelling (F, S, I), fatigue (F, I), decreased appetite (S, I), anxiety (F, SI, I), feelings that nothing could cheer you up (F, S, I), insomnia (S, I), sad or unhappy feelings (F,S, I), hiccups (F, S), hives (P), itchy skin (S), and rash (P) will be rated by patients using the PRO-CTCAE, which has recently been translated and validated in Spanish (Arnold *et al.* 2016, Basch *et al.* 2014, Bennett *et al.* 2016, Dueck *et al.* 2015). F = frequency, S = severity, I = interference with usual or daily activities, P = presence.

⁹Patients will be asked about their dyspnea (worse, about the same, or better) to compare the level of dyspnea before and after the study (Guyatt *et al.* 1993, Redelmeier *et al.* 1996).

¹⁰We will assess adherence by pill count on day 7 and day 14. We will also examine the success of blinding by asking patients to guess which treatment was given (“dexamethasone,” “placebo,” or “do not know”).

¹¹If patient available, otherwise, a phone call or other remote method will be conducted to administer the questionnaires.

E. Statistical Analysis

E.1. Sample size calculation. We will use 2:1 randomization as outlined in Section D.1.2.8. With a two-sided 5% alpha, normally distributed data, equal variance between treatment groups, and a within-group standard deviation of 2.0 (based on our preliminary data; Section D.1.1.3), we will need a total of 174 (116 + 58) patients to have 80% power to detect a mean difference of 1.0 between treatment groups. Assuming 15% attrition, we will need to enroll 134 patients in the dexamethasone arm and 67 in the placebo arm (201 total).

E.2. Data analysis

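### Enrolling 201 leaves about 171 patients after 15% attrition, not the 174 that E.1 says are needed; power barely changes, but the basis for 174 also needs stating

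*Combined protocol and SAP*

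**What the plan says.** Section E.1 sets the allocation ("We will use 2:1 randomization as outlined in Section D.1.2.8") and the test assumptions ("With a two-sided 5% alpha, normally distributed data, equal variance between treatment groups"), with "a within-group standard deviation of 2.0 (based on our preliminary data; Section D.1.1.3". From these it concludes: "we will need a total of 174 (116 + 58) patients to have 80% power to detect a mean difference of 1.0 between treatment groups". It then adds the allowance for loss: "Assuming 15% attrition, we will need to enroll 134 patients in the dexamethasone arm and 67 in the placebo arm (201 total". How 174 becomes 201 is not shown.

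Section D.1 repeats the enrolment figure: "We plan to enroll 201 patients (134 in the dexamethasone group and 67 in the placebo group". Section E.2.3 carries the pre-attrition number for the active arm into the predictor power statement: "With 116 dexamethasone-treated patients".

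Section E.2.1 bears on what a lost patient costs. The primary analysis includes everyone randomised who started treatment, and a missing primary outcome is handled by multiple imputation.

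Two pilot figures are relevant. Section C.3 reports that 35 of 41 randomised patients (85%) completed the blinded phase. In Table 1 the day-7 row for the dyspnea score begins "Day 7 | 16 | 3.6 (2.6) | -1.8 (-3.2 to -0.3), P = 0.02 | 14 | 3.3 (2.1", which is 16 + 14 = 30 observed scores, against 19 + 19 = 38 at baseline.

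**The concern.** An allowance for attrition has to be set so that the required number remains after the loss. If a fraction d is lost, enrolment must be n / (1 - d). Multiplying by (1 + d) falls short, because the loss applies to the larger, enrolled number. The E.1 figures look like the second calculation. If so, the paragraph promises a number that its own attrition rate does not deliver, and the 116 in E.2.3 inherits the discrepancy.

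What is at stake is the consistency of the sample-size paragraph in a trial that presents itself as confirmatory, and possibly the 80% power statement. Whether power is affected depends on how much slack 174 contains, so 174 has to be checked as well.

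**Working it through.** **Inputs.** From E.1: two-sided alpha 0.05, SD 2.0, difference 1.0, power 80%, ratio 2:1, 116 + 58 = 174 required, attrition 15%, 134 + 67 = 201 enrolled. I use *evaluable* for a patient with an observed day-7 score; the label is mine.

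**1. Reproduce the enrolled figures.**
- Multiplying by 1.15: 116 x 1.15 = 133.4, up to 134; 58 x 1.15 = 66.7, up to 67; 174 x 1.15 = 200.1, up to 201. All three stated figures match exactly.
- Dividing by 0.85: 116 / 0.85 = 136.5, up to 137; 58 / 0.85 = 68.2, up to 69; 174 / 0.85 = 204.7, up to 205. Summed by arm this is 206, or 207 if exact 2:1 is kept (138 + 69). None matches.

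The 1.15 multiplier is therefore an inference, though a close one.

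**2. What 201 delivers.**
- 201 x 0.85 = 170.85; by arm 134 x 0.85 = 113.9 and 67 x 0.85 = 56.95, so about 114 + 57 = 171.
- Attrition at which 201 still leaves 174: 1 - 174/201 = 13.4%.
- At the pilot's completion rate: 201 x 35/41 = 171.6, also below 174.

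**3. Effect on power.** Two-sample t-test, noncentrality = difference / [SD x sqrt(1/n1 + 1/n2)].
- 116 + 58: 1.0 / [2.0 x sqrt(1/116 + 1/58)] = 3.11; power 87.1%.
- 114 + 57: 1.0 / [2.0 x sqrt(1/114 + 1/57)] = 3.08; power 86.5%.

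The shortfall costs about 0.6 percentage points. A simulation with the E.2.7 boundaries (normal statistic, looks at one third and two thirds of the information, futility p-values read as two-sided and binding) gives about 85.9% at 116 + 58 and 85.3% at 114 + 57.

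**4. Does 174 follow from the inputs?**
- Placebo arm: n = (1 + 1/2) x [2.0 x (1.960 + 0.842) / 1.0]^2 = 47.1, up to 48; dexamethasone arm 96; total 144. The t-test at 96 + 48 has 80.2% power.
- So the stated inputs need 144, not 174. The interim looks do not explain the gap, since power at 174 is still about 86% with them.
- Three changed input sets give 174: SD 2.2 with a t-test, two-sided alpha of 0.025, or power of 87%. None is what E.1 states.
- If SD 2.2 was the true basis (an assumption), power is 80.3% at 116 + 58 and 79.6% at 114 + 57.

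**5. The other power statements.**
- E.2.2's effect size of 0.5 is 1.0 / 2.0, the same calculation as step 3, so it holds.
- E.2.3 gives odds ratio 2.5, response 30% and correlation 0.30. If one unit is one SD of the marker (an assumption), the usual logistic formula gives (1.960 + 0.842)^2 / [0.30 x 0.70 x (ln 2.5)^2 x (1 - 0.30^2)], about 49 patients. Either 114 or 116 is ample.

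**6. Sensitivity to missing day-7 scores at the pilot's rate, SD 2.0.**
- 30 of 38 with a baseline: 201 x 30/38 = 158.7, about 106 + 53; power 84.0%.
- 30 of 41 randomised: 201 x 30/41 = 147.1, about 98 + 49; power 81.0%.

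**The case against.** The strongest reply is that nothing of substance fails. Three patients is 1.7% of 174, no stated power claim falls below its level under the plan's inputs, and multiple imputation keeps treated patients in the analysis set. This stands as to size. It does not make 201 consistent with 174 at 15% attrition. Imputation keeps a patient in the analysis but does not fully restore the information lost with an unobserved score, and E.2.1 specifies it for the primary outcome, not for the E.2.3 regression.

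Three stronger readings are tempting, and the documents do not support them.
- **That the trial is underpowered, or must enrol more.** Under the stated inputs even 147 observed scores give 81.0%. Power at 171 falls below 80% only if 174 rested on inputs other than those stated, and then by a fraction of a point in the SD 2.2 example.
- **That the pilot shows 15% to be wrong.** The pilot does have fewer day-7 scores (30) than completers (35). But E.1 cites the preliminary data only for the SD, so the link from the 85% completion rate to the 15% is inferred. This trial also adds payment for the day-7 assessment (D.3), and a window of 7 ± 2 days, near-daily contact and a remote fallback (Table 3 and its footnote 11). The pilot rate is a sensitivity figure, not a forecast.
- **That the day-7 SDs in Table 1 (2.6 and 2.1) overturn the power claim.** That concerns the SD assumption, not attrition. Those SDs are unadjusted, while the primary model adjusts for baseline, and the same table shows smaller values at baseline (2.1 and 1.5) and day 4 (1.8 and 2.0).

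**Conclusion.** The discrepancy is real and small. At the plan's own 15% attrition, 201 enrolled leaves about 171 (114 + 57), three fewer than E.1 says are needed. The loss of power is about 0.6 points, and the 80% statement holds under the stated inputs.

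The larger gap in the same paragraph is between 174 and its inputs: 80% power needs 144, and 174 gives 87.1%. Until the basis for 174 is stated, a reader cannot tell whether the slack is deliberate or whether a different SD, alpha or power target was used. Only in the latter case might the attrition slip bring power to the margin.

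These conclusions rest on reading attrition as loss of the day-7 score, on an unadjusted two-sample t-test, and on inferring the 1.15 multiplier. The shortfall itself (201 x 0.85) does not depend on that last inference.

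**What to change.** In E.1:
- State that 201 enrolled gives about 171 evaluable patients (114 + 57) at 15% attrition, or that 201 tolerates attrition up to 13.4%.
- Give the power at that number: 86.5% if the inputs in E.1 are the intended ones.
- State the inputs that produced 174, or correct the inputs or the figure so that they agree. If a larger SD was used, report the matching power at 171.

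In E.2.3, change 116 to 114. The enrolment figure in D.1 can stay.

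Optionally, report power at the pilot's share of missing day-7 scores (about 84% and 81% at SD 2.0), labelled as a sensitivity figure, with a note that multiple imputation and remote follow-up may reduce that loss.

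The cost is a few sentences. No extra patients are needed, and the only concession is a slightly less favourable evaluable number.
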